3.3 Subject Early Termination

Subject early termination reasons including deaths, withdrawals, lost-to-follow-up, etc. will be summarized for all enrolled subjects.

Statistical Analysis Plan

3.4 Protocol Deviation

Protocol deviations will be summarized by category for subjects in whom a protocol deviation was reported. Number of protocol deviations and number of subjects with deviation will be summarized by deviation categories.

3.5 Descriptive Endpoints or Additional Data

3.5.1 Descriptive Endpoints

The descriptive endpoints will be analyzed in a PTE fashion. Subjects will be analyzed at each visit by the treatments they received. For example, for NRS, there will be a summary at each visit by the treatments received.

Descriptive endpoints include:

- Proportion of patients who elect to cross-over after the primary endpoint
- Change from baseline at each time point on the following:
 - ODI
 - NRS
 - PROMIS-29 questionnaire
 - Pain Catastrophizing Scale (PCS)
 - Pain-condition related medication usage
 - Exercise frequency
- Healthcare resource utilization
- Device programming and usage
- Patient satisfaction with therapy
- Patient Global Impression of Change (PGIC)
- Serious device-related adverse events

Responder analysis:

- Proportion of subjects with $\geq 30\%$ decrease on NRS
- Proportion of subjects with $\geq 50\%$ decrease on NRS
- Proportion of subjects with $\geq 13\%$ -point improvement, at least one category improvement or score $\leq 20\%$ on ODI
- Proportion of subjects within 1 SD of population norm or reach MCID on PROMIS-29 domains
 1. For the within 1 SD of population norm component:
 - Lower scores are better for negatively worded domains, like anxiety
 - Responder: needs a T-score of ≤ 60
 - Higher scores are better for positively worded domains, like physical function
 - Responder: needs a T-score of ≥ 40
 2. For the MCID component
 - MCIDs will be based on literature
- Proportion of subjects that are either clinically catastrophizing on PCS at baseline (PCS score ≥ 30) and report a score of < 30 at follow up or report a 40% decrease in score at follow-up compared to baseline.

Statistical Analysis Plan

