6.5 Spinal Cord Stimulation (interventional arm)

A successful trial, defined as 50% decrease in pain recorded on Numerical Rating Scale is required for a subject to receive a permanent implant.

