6.6.4 Crossover

Crossover prior to the study primary endpoint is not allowed. To ensure valid analysis of all endpoints, investigators and coordinators must make concerted efforts to prevent crossover from CMM to SCS prior to completing the 6-month visit. If a subject is unwilling to complete the assigned treatment, they should be withdrawn. Upon completion of the 6-month primary endpoint visit, a subject is allowed to crossover to the other arm. The permanent implant must occur prior to the [REDACTED] follow up visit.

Clinical Investigation Plan

Subjects crossing over to the SCS arm will follow the trial and permanent SCS procedures as part of standard of care. Upon receiving a permanent implant, subjects will continue to participate in the study according to Section 6.6. The follow-up timeline will not be reset; the subject will continue with the follow-up schedule. Subjects are not allowed to crossover more than once.

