8.2.3 Descriptive Endpoint(s) Analyses

Descriptive summary statistics will be presented for the descriptive endpoints within each treatment group. Continuous variables will be summarized using mean, standard deviation, median, minimum, and maximum. Categorical variables will be summarized using [REDACTED]. Time-to-event variables will be analyzed using the [REDACTED]. The 95% confidence intervals for each type of data will be provided as appropriate.

Difference between groups will be summarized using descriptive statistics including [REDACTED].

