1.3 Clinical Investigation Design

This is a prospective, multi-center, randomized, controlled clinical trial with an optional crossover component. It is designed to evaluate the efficacy of BurstDR™ Spinal cord stimulation (SCS) in the treatment of chronic axial low back pain with a neuropathic component, compared with comprehensive medical management (CMM).

Subjects will be followed in-clinic for required study visits at 1,3, 6, 9, 12, 18 and 24 months and via phone call or optional clinic visit at 15- and 21-months. Due to the individualized nature of study therapies, patient reported outcomes will be continually assessed and additional patient outreach conducted in order to determine if therapy adjustment(s) are warranted to optimize pain control. The primary endpoint will be assessed at the 6-month follow-up visit. Upon completion of the 6-month follow-up visit, subjects who are dissatisfied with therapy and receiving inadequate improvement with their treatment assignment will be allowed to cross-over to the other treatment arm, if desired per Cross Over Instructions (CL1014686).

Up to 270 subjects will be randomized in the study which is split into two phases. Phase I will include the first minimal 200 randomized subjects. Phase II is the continued access phase and will include up to 70 randomized subjects.

Subject enrollment is expected to be completed within 18 months; subjects will be followed for 2 years. The total duration of the study is expected to be approximately 4 years, including enrollment, data collection from all subjects, and study close out.

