2.0 ANALYSIS CONSIDERATIONS

2.1 Analysis Populations

The analysis populations include:

1. Intention-to-Treat (ITT) Population: includes all randomized subjects. Subjects will be analyzed according to the treatment group they are randomized to. The ITT population will be used as the primary analysis population for the primary endpoint.
2. Modified Intention-to-Treat (mITT) Population: includes all randomized subjects except for those who are randomized to the SCS group who fail the trial period, do not receive a permanent system implant. Subjects will be analyzed according to the treatment group they are randomized to.
3. Per-Treatment Evaluable (PTE) Population: includes all subjects in the mITT population who either receive permanent implant or receive CMM. Subjects will be analyzed according to the actual treatment received. The PTE population will be used as the primary analysis population for the study except the primary endpoint analysis.

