2.4 Sample Size/Power Calculations

The study was designed to enroll approximately 200 subjects in Phase I and up to 70 subjects in Phase II. The following assumptions are used in the power calculation for the primary endpoint:

- Assumed response rate of 45% for the SCS group and 20% for the CMM group
- 3:2 (SCS:CMM) randomization ratio
- 25% attrition rate to primary endpoint (6 months) follow-up in both groups
- Two-sided alpha of 0.05
- Z-test with unequal variance

Based on the assumptions above, there is at least 90% power to evaluate the primary endpoint with the Phase I cohort.

The minimum detectable differences for secondary endpoints using phase I PTE cohort (assume approximately 80 SCS and 60 CMM) with 80% power are shown in Table 1 below.

Table 1: Minimum Detectable Differences (MID) for Secondary Endpoints

Secondary Endpoints	MID (standard deviation for each group)
#1: Composite Responder	23%
#2: Relative NRS Change in %	16.9(35)
#3: ODI Change	7.2 (15)
#4: PCS Responder	21%
#5: PGIC (%)	23%
#6: Relative Pain Interference Change in %	7.2 (15)
#7: Relative Physical Function Change in %	12.0 (25)

The sample size re-estimation will be based on the interim analysis (IA) population (Adaptive Design Plan CL1014964). The unblinded independent statistician will perform the sample size re-estimation for 4 endpoints (1 primary and secondary endpoints #1, #2, and #3) and generate a recommendation if more subjects are needed to meet the statistical significance of each endpoint.

The power calculation was performed using PASS 15 (NCSS LLC).⁵

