3.5.2 Additional Analyses

An additional analysis will be performed for the subjects who crossed over from CMM to SCS after 6 months primary endpoint assessment. The analyses will be done by paired comparison (SCS crossover - CMM baseline value) at each visit. The p-value will be displayed for descriptive purpose.

In addition, the following analysis will be conducted on the PTE population for the primary endpoint:

- For the subjects with opioid medication increase (based on CDC dose markers, ≥ 90 MME daily if taking for at least 5 days within two weeks prior to 6 months visit), they will be considered as non-responders regardless their received treatment.

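### After month 6, the descriptive tables by treatment received give crossovers no column of their own, so on the plain reading the SCS rows mix times since implant and the CMM rows hold a selected group

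*SAP*

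**What the plan says.** SAP 3.5.1 applies the PTE approach to the descriptive endpoints and sets the grouping rule: "Subjects will be analyzed at each visit by the treatments they received". It uses NRS as its example. SAP 2.1 defines the PTE population as one that "includes all subjects in the mITT population who either receive permanent implant or receive CMM", analysed by actual treatment. That gives two treatment categories and no crossover category.

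Crossover opens after the month-6 visit. SAP 1.3 says that "subjects who are dissatisfied with therapy and receiving inadequate improvement with their treatment assignment will be allowed to cross-over to the other treatment arm", so it can run in either direction, and Protocol 3.0 gives the same condition. Protocol 6.6.4 allows crossover after month 6 without stating that condition. On timing it says: "The follow-up timeline will not be reset; the subject will continue with the follow-up schedule". A CMM subject moving to SCS goes through the trial and implant steps, and under Protocol 6.5 a successful trial "is required for a subject to receive a permanent implant". Protocol 6.6.4 also sets a latest visit for the crossover implant, but that visit is redacted.

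Two other analyses touch on crossovers or later visits. SAP 3.5.2 adds one for CMM-to-SCS crossovers: "The analyses will be done by paired comparison (SCS crossover - CMM baseline value) at each visit". SAP 2.2.4.2 allows exploratory mixed models of repeated outcomes. For the descriptive endpoints, Protocol 8.2.3 plans summaries within each treatment group and adds: "Difference between groups will be summarized using descriptive statistics". No summary by randomised arm after month 6 is specified.

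**The concern.** Two separate things happen to the rows after month 6 if the rule is followed as written.

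The first is exposure. A crossover implanted after month 6 keeps the original visit calendar. At the month-12 visit such a subject would stand in the SCS row beside subjects with up to about a year of stimulation. A row read as the durability of SCS would then mix early and late times since implant.

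The second is selection. Under SAP 1.3, crossover is open to subjects who did poorly by month 6. If those subjects leave, the CMM row can look better although nobody has improved. SCS-to-CMM crossovers would also leave the SCS row and enter the CMM row. A descriptive SCS-minus-CMM difference at month 12 or 24 would then compare groups re-sorted by the month-6 result.

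These tables support no success claim. They do cover most of a two-year follow-up, and readers will look to them for longer-term effectiveness.

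**Working it through.** **No plan figure to reproduce.** The documents give no crossover rate and no expected trial success among crossovers. The row sizes below come from SAP 2.4 ("assume approximately 80 SCS and 60 CMM", Phase I PTE cohort). The CMM figure agrees with the SAP's other inputs: 200 × 2/5 × (1 − 0.25) = 60.

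**Step 1: exposure gap.** Take the SCS clock as starting at implant, and assume that the crossover is implanted straight after the month-6 visit. Stimulation time is then the visit month for randomised SCS and the visit month minus 6 for crossovers.

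| Visit | Randomised SCS | Crossover, nominal |
|---|---|---|
| 9 | 9 months | 3 months |
| 12 | 12 | 6 |
| 18 | 18 | 12 |
| 24 | 24 | 18 |

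The nominal gap is 6 months. Three things move it:
- A 4-day trial (the minimum in Protocol 6.5.2) plus the 45-day limit to implant (6.5.4) adds 49/30.44 = 1.6 months, giving about 7.6.
- A month-6 visit held 30 days early, if the ±30-day window applies, takes off about 1 month, giving about 5.
- Protocol 6.6.1 and 6.6.3 time visits from randomisation or implant. If the SCS clock starts at randomisation and the implant delay is equal in both groups, the gap is 6.0.

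A later decision to cross over widens the gap, up to the redacted implant deadline. The month-9 row may hold few crossovers, because trial and implant come first.

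**Step 2: share of the SCS row (illustration).** Assume 80 randomised SCS and 60 CMM subjects, no later attrition and no SCS-to-CMM crossover. Let a = 60 × the proportion choosing crossover and x = a × trial success. The share is x/(80 + x).

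| Choosing crossover | a | x at 60% / 100% trial success | Share of SCS row |
|---|---|---|---|
| 30% | 18 | 10.8 / 18 | 11.9% / 18.4% |
| 50% | 30 | 18 / 30 | 18.4% / 27.3% |
| 70% | 42 | 25.2 / 42 | 24.0% / 34.4% |

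At 50%, the mean nominal time since implant in the month-12 row is (80 × 12 + 18 × 6)/98 = 10.9 months, or (80 × 12 + 30 × 6)/110 = 10.4 months, against 12 with no crossovers.

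**Step 3: CMM row (illustration).** Start from the SAP's assumed 20% response, so 12 responders and 48 non-responders. Hold everyone's month-6 response fixed. The main figures assume that all who choose crossover leave the row. Those in brackets assume 60% trial success, with the trial failures kept in the row.

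| Choosing crossover | Unrelated to response | Responders cross at half the rate | Only non-responders cross |
|---|---|---|---|
| 30% | 20% (20%) | 23.8% (22.0%) | 28.6% (24.4%) |
| 50% | 20% (20%) | 28.9% (23.8%) | 40.0% (28.6%) |
| 70% | 20% (20%) | 40.7% (26.4%) | 66.7% (34.5%) |

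Worked for 50%:
- Only non-responders cross: 12/30 = 40.0%, or 12/42 = 28.6% with trial failures kept.
- Half rate: non-responders cross at 30/(48 + 6) = 0.556 and responders at 0.278. The row is (12 − 3.33)/30 = 28.9%. With failures kept it is (12 − 2.0)/42 = 23.8%.

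Whether subjects who fail a crossover trial stay in the CMM row is not settled. Protocol 6.6.4 describes continued participation only after implant, and SAP 2.3.1.1 refers to trial failures who withdrew.

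**The case against.** The strongest reply is that the SAP never says crossovers share a column with randomised SCS. The rule speaks of treatments in the plural, SAP 3.5.2 already treats CMM-to-SCS crossovers as a group, and a programmer could give them their own column. This stands in part. A reader might infer that the SAP expressly orders pooling, and it does not. But the PTE definition offers two categories, and nothing adds a third or takes crossovers out of the SCS row. Pooling is therefore the plain reading.

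Second, other output exists. The paired analysis describes CMM-to-SCS crossovers at each visit, the proportion electing crossover is reported, and mixed models may be fitted. So these tables are not the only output after month 6. None of it corrects them, however. The paired analysis covers one direction and leaves the rows unchanged. The mixed models are optional and do not say how crossovers are classed.

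Third, the selection argument rests on the condition in SAP 1.3 and Protocol 3.0. Protocol 6.6.4 omits it, and the crossover instructions that SAP 1.3 cites are not among the documents. This is fair, and those passages need reconciling. Even without the condition, crossing over is the subject's choice and is likely to relate to how the subject is doing.

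Finally, describing results by treatment received is a legitimate choice when nothing is tested, and it suits items such as device programming and usage. That stands, and the fix keeps it for those items.

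**Conclusion.** The point holds as a minor one. Followed as written, the rule in SAP 3.5.1 would on its plain reading mix times since implant in the SCS rows after month 6 and leave a CMM group partly selected on the month-6 result. The exposure difference is nominally about 6 months, roughly 5 to 8 for a subject who proceeds promptly.

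Two stronger readings are tempting and are not supported:
- That crossovers always have at least 6 months less stimulation. Six months is a nominal figure, and an early month-6 visit could bring it to about 5.
- That the trial's main conclusion is biased. Crossover is barred before the month-6 visit, so the primary and secondary tests at month 6 are untouched.

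The size of the effect cannot be computed. At 50% crossover, the share of the SCS row is 18% to 27% and the CMM response reads 20% to 40%. These figures rest on assumed crossover and trial-success rates, no later attrition, no SCS-to-CMM crossover and fixed month-6 response. The range includes no distortion of the CMM row at all.

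**What to change.** In SAP 3.5.1, for visits after month 6:
- Report outcome endpoints in separate columns: randomised SCS, CMM remaining on CMM, CMM-to-SCS crossovers, and any SCS-to-CMM crossovers.
- State the column for crossovers who are not implanted.
- For CMM-to-SCS crossovers, give the distribution of time since implant at each visit.
- Add a summary by randomised arm at each visit. It describes the assigned strategies including crossover, so it complements the separate columns.
- Keep tables by treatment received for items such as device programming and usage.

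The cost is SAP wording and a few extra tables from data already collected, with no new visits or subjects. The smaller columns will have wider intervals. Because crossovers stay on the original calendar, their time since implant will not line up with scheduled visits and can only be shown as a distribution.

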5.3.2 Inclusion Criteria

1. Patient must be willing and able to provide written informed consent prior to any clinical investigation-related procedure.
2. Age \geq 18 years
3. Patient has chronic (at least 6 months), refractory axial low back pain with a neuropathic component and is not a candidate for spine surgery
4. Patient has back pain for \geq 6 months inadequately responsive to supervised conservative care
5. Patient has not had spine surgery for back or leg pain
6. Patient is a candidate for spinal cord stimulation
7. Low back pain \geq 6 on Numerical Rating Scale
8. Oswestry Disability Index score of \geq 30%
9. Willing and able to comply with the instructions for use, operate the study device, and comply with this Clinical Investigation Plan

This confidential document is the property of Abbott and shall not be reproduced, distributed, disclosed or used without the express written consent of Abbott

Clinical Investigation Plan

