6.6.2.5 Oswestry Disability Index (ODI)

The ODI is an index derived from the Oswestry Low Back Pain Questionnaire used by clinicians and researchers to quantify disability for low back pain (26). The self-completed questionnaire contains ten topics concerning intensity of pain, lifting, ability to care for oneself, ability to walk, ability to sit, sexual function, ability to stand, social life, sleep quality, and ability to travel. Each topic category is followed by 6 statements describing different potential scenarios in the subject's life relating to the topic. The subject checks the statement which most closely resembles their situation. Each question is scored on a scale of 0-5 with the first statement being zero and indicating the least amount of disability and the last statement is scored 5 indicating most severe disability. The scores for all questions answered are summed, divided by the total possible score based on the number of questions answered and converted to a percentage. Zero is equated with no disability and 100 is the maximum disability possible. Five different levels of disability are defined within that range; minimal (0%-20%), moderate (21%-40%), severe (41%-60%),

Clinical Investigation Plan

crippling (61%-80%), and bed bound or exaggerated symptoms (81-100%). A decrease of 13% or more on the 0%-100% scale demonstrates a meaningful, clinical improvement in disability (27).

6.6.2.6 Patient-Reported Outcome Measure Information System (PROMIS) 29

The PROMIS-29 is a 29-item profile instrument developed in partnership with the National Institutes of Health (NIH) to estimate overall quality of life by assessing 7 health domains known to impact activities of daily living: depression, anxiety, physical function, pain interference, fatigue, sleep disturbance, and social function. The final item is an 11-point pain intensity numerical rating scale (NRS). Subjects should read each item and check the one box that most closely represents their response. Each item is scored on a scale from 1-5 with total scores for each domain ranging from 4-20. Greater scores represent more of whatever concept is being measured (e.g., depression or physical function). Scoring tables have been provided in the measure manual. Raw domain scores are converted to t-scores with a mean of 50 and a standard deviation of 10.

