15.0 RISK ANALYSIS

15.1 Anticipated Clinical Benefits

Published literature on current treatment options for patients with chronic, intractable, low back pain report mild, if any, improvements in pain and physical function. [REDACTED]. A recent review of opioid therapy in subacute and chronic low back pain concluded even though opioids reduce pain intensity, non-opioid treatments in these studies show a statistically significant greater reduction. Furthermore, improvements in pain relief are outweighed by harms associated with opioids (30). Deterioration in functional outcomes has also been associated with opioid therapy in low back pain populations (31).

In contrast, small case series report significant improvements in pain and function using various spinal cord stimulation systems in this population (19, 32). On average, pain is reduced by over 70% and disability is reduced to a minimal level (average ODI < 20%). These small studies provide support for investigating the effect of SCS in this population. In addition, the unique mechanism of action of BurstDR provides the ability to evaluate improvement in psychometric measures.

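### The norm branch of the descriptive PROMIS-29 responder rule has no baseline condition, so the responder rate is not a rate of improvement

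*SAP*

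**What the plan says.** SAP 3.5.1 (Descriptive Endpoints), under its responder analyses, counts the "Proportion of subjects within 1 SD of population norm or reach MCID on PROMIS-29 domains". Protocol 4.3 lists the same item. The SAP then makes the two branches operational:

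- Norm branch, negatively worded domains such as anxiety: "Responder: needs a T-score of ≤ 60".
- Norm branch, positively worded domains such as physical function: "Responder: needs a T-score of ≥ 40".
- MCID branch: "MCIDs will be based on literature", with no values given.

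Neither document ties the norm branch to the baseline score, and no eligibility criterion in Protocol 5.3 uses PROMIS-29. The instrument is collected at baseline (Protocol 6.2.2).

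Two neighbouring rules in the same list are protected. The cut-off branch of the PCS rule applies only to subjects with a baseline score of 30 or more. The ODI target of 20% or less cannot already be met at an eligible baseline, because entry requires an ODI of at least 30%.

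**The concern.** A responder rate is normally read as the share of subjects who got better. Here one of the two routes to response is a state at the visit, and a subject can hold that state from the start. A move from T = 50 to T = 59 on anxiety is 9 points, or 0.9 SD, in the wrong direction, and it still counts as a response.

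Two things follow. First, the within-arm rate mixes improvement with the case mix at enrolment, and the mixture differs by domain. Second, subjects who would count in either arm add the same amount to both rates and leave less room for a treatment difference to appear.

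The objective is framed as improvement. Protocol 15.1 also says that "the unique mechanism of action of BurstDR provides the ability to evaluate improvement in psychometric measures". Anxiety and depression are not among the PROMIS secondary endpoints, so this list holds the only PROMIS responder analysis for them.

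**Working it through.** **1. The plan's own figures.** Protocol 6.6.2.6 states: "Raw domain scores are converted to t-scores with a mean of 50 and a standard deviation of 10". One SD either side of the norm is 50 + 10 = 60 and 50 − 10 = 40. The SAP cut-offs reproduce exactly, so the cut-offs are not at fault.

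**2. Assumptions.** The documents give no baseline PROMIS-29 distribution and no MCID. For one negatively worded domain, assume:

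- true score normal with mean *m* and SD 8;
- independent measurement error with SD 3 at each visit;
- MCID of 5 points;
- *m* = 50, 55, 60 or 65.

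The observed SD is then √(64 + 9) = √73 = 8.54. The baseline/follow-up correlation is 64/73 = 0.88. The SD of the observed change is √(9 + 9) = 4.24. A positively worded domain is the mirror image around 50.

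**3. Zero true change.**

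- In range at baseline: Φ((60 − *m*)/8.54).
- MCID reached by error alone: 1 − Φ(5/4.24) = 12%, whatever *m* is.
- Rule as written: P(follow-up ≤ 60) + P(follow-up > 60 and fall ≥ 5).
- Rule with a baseline condition: P[(baseline > 60 and follow-up ≤ 60) or fall ≥ 5], by simulation.

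**4. A true benefit of 6 points in one arm only.** The same expressions apply with follow-up shifted down by 6. Gaps are taken before rounding.

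| Baseline mean | In range at baseline | As written, no change | As written, 6-point benefit | Gap as written | Conditioned, no change | Gap conditioned |
|---|---|---|---|---|---|---|
| 50 | 88% | 89% | 98% | about 10 | 14% | 47 |
| 55 | 72% | 74% | 94% | 20 | 15% | 47 |
| 60 | 50% | 54% | 87% | 33 | 16% | 48 |
| 65 | 28% | 35% | 78% | 43 | 15% | 48 |

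At mean 55 with no true change, about 33% of all subjects score numerically worse at follow-up and are still counted as responders.

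**5. Other assumptions.** A correlation of 0.88 is high, so the check was repeated with lower correlations.

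- Zero change, correlation 0.5–0.7, MCID 3–5. Baseline mean 52, SD 9: 83–84% as written against 26–38% conditioned. Mean 58, SD 9: 64–67% against 27–38%. Mean 65, SD 7: 34–43% against 21–35%.
- A 6-point benefit, correlation 0.6, MCID 4. Gaps of 12, 22 and 38 points as written at means 52, 58 and 65, against 28, 28 and 37 conditioned.

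The pattern is the same: heavy dilution near the norm, little or none in a clearly impaired domain.

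**The case against.** The strongest reply is that little depends on this item. It is descriptive, outside the testing hierarchy (SAP 2.11) and outside the success criterion (SAP 2.7). PROMIS-29 change from baseline is reported at every time point in the same section. Pain Interference and Physical Function are tested as relative change in secondary endpoints #6 and #7. All of this stands, and it limits the severity.

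A reader might infer that the rule cannot show improvement at all, that rates will be high in both arms, or that real differences will be swamped. The documents do not support any of these. The MCID branch requires change from baseline. A subject in range at baseline must still be in range at follow-up. The gap between arms does move with a true effect, and at a baseline mean of 65 it is nearly intact. How high the rates run depends on baseline values that the documents do not give. The exclusions for untreated mental illness and failed psychological evaluation make near-normal anxiety and depression scores plausible, but do not establish them.

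A reader might also extend the point to the ODI category-improvement branch in the same list. That branch does require change from baseline, so it does not share this fault.

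The contrast of 74% with 15% at mean 55 is fairly called one favourable scenario. With lower correlation, the conditioned rate at zero change is 21–38%. What the reply does not answer is the label: subjects who are unchanged or worse are counted as responders.

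**Conclusion.** The point holds for the norm branch of the PROMIS-29 responder rule, as a minor one. That the branch is a follow-up status with no baseline condition is a matter of text and needs no assumption. The within-arm rate therefore cannot be read as a rate of improvement.

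The size rests on assumed baseline distributions, correlations and MCIDs. With SD 8, error SD 3 and MCID 5, the zero-change rate is 35–89% across baseline means of 65 down to 50, where a baseline-conditioned rule gives 14–16%. A 6-point benefit shows as a gap of about 10 to 43 points, where the conditioned rule gives 47–48. The loss is greatest in near-normal domains and small in impaired ones. No confirmatory conclusion of the trial depends on it.

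**What to change.** In SAP 3.5.1 and Protocol 4.3:

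1. Define a domain responder as a subject who either (a) has baseline T > 60 and follow-up T ≤ 60 on a negatively worded domain, or baseline T < 40 and follow-up T ≥ 40 on a positively worded one, or (b) improves from baseline by at least the domain's MCID. Part (a) follows the form that the PCS rule already uses.
2. List the MCID for each domain, with its source, before the analysis.
3. Report the proportion in range at baseline, by arm and domain, beside each responder rate.

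The cost is wording and programming; no new data are needed. Reported responder rates will fall in both arms. Subjects near the best possible score at baseline cannot meet (a) and may be unable to meet (b), so they will count as non-responders. Item 3 makes their share visible.
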